## TECHNICAL SUMMARY REPORT (TSR)

Name of Sponsor/Company Glenmark Specialty SA
Name of Investigational Product: GSP304 (tiotropium bromide) Inhalation Solution
Name of Active Ingredient: Tiotropium Bromide
Title Of Study: A Dose Ranging, Parallel Group, Active (Spiriva® Respimat®) and Placebo-controlled Study to Assess Relative Bioavailability, Pharmacodynamics and Safety of Three Doses of Tiotropium Bromide Inhalation Solution in Subjects With Mild to Moderate Chronic Obstructive Pulmonary Disease
Phase of development: Phase 2
Objectives: Primary: To assess the relative bioavailability of GSP304 (tiotropium bromide) Inhalation Solution at dose levels of [REDACTED] compared with Spiriva® Respimat® inhalation spray (5 µg QD) in subjects with COPD. To characterize the dose response of GSP304 at dose levels of [REDACTED] with respect to pharmacodynamics (PD). Secondary: To assess the safety and tolerability of GSP304 at dose levels of [REDACTED]
Methodology: This is a phase 2, randomized, parallel group, active- and placebo-controlled, 5-arm study to compare the PK profile of 3 blinded doses of GSP304 with open label Spiriva® Respimat®. The study will also evaluate the dose response PD profile of 3 blinded doses of GSP304 compared with blinded GSP304 placebo, using spirometry in subjects with mild to moderate COPD. A total of 155 male and female subjects will be randomized in a 1:1:1:1:1 ratio to 1 of 5 treatment arms. A subject will receive 1 of the 3 double-blind doses of GSP304, or double-blind GSP304 placebo, or open-label Spiriva® Respimat®. The study will include a screening period of up to 2 weeks, followed by a 2 week run-in period, 3 weeks of treatment, and a 2 week post treatment follow up period. The total duration of study participation will be approximately 9 weeks. In this study, PK of tiotropium in plasma and urine will be assessed on Day 1 and Day 21 (at steady state).
Number of Subjects (planned): A total of 155 subjects will be randomized in this study.
Study Endpoints: Primary Endpoint 

• The PK endpoints for tiotropium in plasma to assess the relative bioavailability are:

• Peak concentrations during the dosing interval at steady-state (<math>C_{max,SS}</math>)

• Area under the plasma concentration-time curve over the dosing interval at steady state (<math>AUC_{0-\tau,SS}</math>)

• Change from baseline (Day 1) at Day 21 (Week 3) in trough FEV1 response at approximately 24 hours after the last dose (average of 23 hours 15 minutes and 23 hours 45 minutes post-dose measurements), in comparison with GSP304 placebo

 Secondary Endpoints 

• Amount (<math>A_{etau}</math>) and fraction of dose (<math>F_e</math>) of tiotropium excreted in urine over the dosing interval on Day 1 and Day 21

• Peak concentrations during the dosing interval (<math>C_{max}</math>) on Day 1

• Area under the plasma concentration-time curve over the dosing interval (<math>AUC_{0-\tau}</math>) on Day 1

• Time of peak drug concentration over the dosing interval (<math>t_{max}</math>) on Day 1 and Day 21

• Average concentration during a dosing interval at steady state (<math>C_{av,SS}</math>) on Day 21

• Accumulation ratio (<math>R_{ac}</math>)

- Change from baseline in peak FEV1 within 12 hours post-dose on Day 1 and Day 21
- Change from baseline (Day 1) at Day 21 (Week 3) in trough FVC response at approximately 24 hours after the last dose (average of 23 hours 15 minutes and 23 hours 45 minutes post-dose measurements), in comparison with GSP304 placebo
- Change from baseline in time-normalized area under the curve for FEV1 measured over 12 hours on Day 1 and Day 21
- Time to onset of response, defined as at least 12% and 200 mL increase in FEV1 within 12 hours of dosing on Day 1
- Time to achieving steady state as measured by FEV1 trough assessments
- Time to achieving steady state as measured by FVC trough assessments

**Safety Endpoints**

- Vital signs, laboratory parameters, 12-lead electrocardiogram (ECG)
- Incidence of all adverse events (AEs)

**Diagnosis and main criteria for inclusion:**

Males and females of non-childbearing potential  $\geq 40$  and  $\leq 85$  years of age with a primary clinical diagnosis of mild to moderate COPD, a FEV1/FVC ratio of  $< 70\%$  and a baseline FEV1 of  $\geq 50\%$  of predicted normal value as per the NHANES III predicted normal values at screening

**Investigational product, dose and mode of administration:**

Name of Investigational Products:

GSP304 (tiotropium bromide) Inhalation Solution, [REDACTED]  
GSP304 (tiotropium bromide) Inhalation Solution, [REDACTED]  
GSP304 (tiotropium bromide) Inhalation Solution, [REDACTED]

Dosage Form: Inhalation Solution

Dosage: Oral inhalation

Dosage Frequency: [REDACTED]

Mode of Administration: By oral inhalation using a nebulizer

**Comparator, dosage and mode of administration:**

Placebo to match GSP304

Dosage Form: Inhalation Solution

Dosage Frequency: [REDACTED]

Mode of Administration: By oral inhalation using a nebulizer

**Reference therapy, dose and mode of administration:**

Name of Comparator: Spiriva® Respimat® inhalation spray 2.5 µg per actuation

Dosage Form: Inhalation Spray

Dosage: 5 µg (2 actuations of 2.5 µg each)

Dosage Frequency: Once Daily (QD)

Mode of Administration: By oral inhalation using Respimat® Soft Mist Inhaler

**Duration of treatment:**

3 weeks (21 days)

**Criteria for evaluation :**

**Efficacy:**

Spirometry

FEV1 and FVC

Refer to 'Pharmacodynamics Assessments' sub-section below.

**Pharmacokinetic, Pharmacodynamics, Biomarker, and Pharmacogenomics Assessments:**

**Pharmacokinetic Assessments**

Blood samples (approximately 6 mL) will be collected in dipotassium ethylenediaminetetraacetic acid (EDTA)

coated vacutainers on Day 1 and Day 21 according to the below schedule: Pre-dose (0 hour), and 2, 4, 6, 10, 15, 30, 45, 60, 75, and 90 minutes post-dose, as well as 2, 4, 6, 8, 12, 16, 20 and 24 hours post-dose. The pre-dose sample on Day 1 should be collected within 30 minutes prior to dosing while on Days 7, 14, and 21 the pre-dose sample should be collected within 10 minutes prior to the morning dose. On Day 1 and Day 21, samples will be collected within the following collection windows:

For the 2 minute sample, within a window of  $\pm 30$  seconds

For the 4, 6, 10, 15, and 30 minute samples, within a window of  $\pm 1$  minute

For the 45, 60, 75, 90 minute, and 2.0 hour samples, within a window of  $\pm 2$  minutes

For the 4, 6, 8, 12, 16, 20 and 24 hour samples, within a window of  $\pm 5$  minutes.

In addition, urine will be collected into pre-weighed containers at pre-dose (within 1 hour prior to dosing), and at the following intervals post-dose from 0-6, 6-12, and 12-24 hours on Day 1 and Day 21.

Collection times and the accurate volume of urine will be noted. In each urine container, approximately 5 mL of 1M citric acid must be added prior to start of collection. Plasma and urine concentrations of tiotropium will be quantified by a validated liquid chromatography-mass spectrometry (LC/MS/MS) method.

#### **Pharmacokinetic Parameters**

##### **Plasma:**

- $AUC_{0-\text{tauSS}}$
- $C_{\text{maxSS}}$
- $C_{\text{minSS}}$
- $C_{\text{avSS}}$
- $C_{\text{max}}$  on Day 1
- $t_{\text{max}}$  on Day 1 and Day 21
- $AUC_{0-\text{tau}}$  on Day 1
- $R_{\text{ac}}$

##### **Urine:**

- $A_{\text{etau}}$
- $F_e\%$

#### **Additional Pharmacokinetics**

Additional parameters may be evaluated depending on the data obtained during the study.

- $t_{\text{last}}$  on Day 1 and Day 21

#### **Pharmacodynamics, Biomarker, and Pharmacogenomics Assessments**

In addition to screening, pre-dose FEV1 and FVC will be assessed at -45 minutes and -15 minutes prior to dosing on Day 1, Day 7, Day 14, and Day 21. Trough FEV1 will be assessed on Day 22 (ie, 24 hours after the Day 21 dose).

On Day 1 and Day 21, FEV1 will be recorded, at the following time points after the morning dose: immediately post-dose at 5 minutes ( $\pm 3$  minutes), 15 minutes ( $\pm 2$  minutes), 30 minutes ( $\pm 5$  minutes), 60 minutes, 90 minutes, and 2 hours (120 minutes); and post-dose at 4, 6, 8, 10, 12, 23 hours 15 minutes and 23 hours 45 minutes post dose. The window for 1-hour spirometry and thereafter is  $\pm 5$  minutes.

Spirometry Effort Start Time is defined as the time of the end of the first effort (Test 1) regardless of whether this is an acceptable effort instead of "start time of first spirometry effort" as described in the protocol.

*FEV1:* FEV1 is the volume of air forcibly exhaled in one second as measured by a spirometer.

*Peak FEV1:* It is defined as the maximum FEV1 over the period of 12 hours post-morning dose.

*Trough FEV1:* It is defined as the mean FEV1 obtained 23 hours 15 minutes and 23 hours 45 minutes post-morning dose of the previous day.

*Baseline FEV1:* It is defined as the average of the pre-dose FEV1 measured at -45 minutes and -15 minutes at Day 1

*FVC:* FVC is the amount of air which can be forcibly exhaled from the lungs after taking the deepest breath possible.

*Baseline FVC:* It is defined as the average of the pre-dose FVC measured at -45 minutes and -15 minutes at Day 1.

#### **Safety:**

Safety assessments will consist of monitoring and recording all Adverse Events (AEs) and serious adverse events (SAEs) including treatment related AEs and SAEs as well as AEs leading to discontinuation, clinical laboratory measurements, vital signs, 12-lead ECG, and physical examinations.

### **Analysis Sets**

#### **Full Analysis Set (FAS)**

This will include all subjects who are randomized, have received at least 1 dose of study medication and have at least 1 post-baseline PD assessment. This analysis set will be the primary analysis set for the PD endpoints.

#### **Safety Analysis Set (SAF)**

This will include all subjects who are randomized and received at least 1 dose of study medication. All safety endpoints will use the SAF unless otherwise specified.

#### **Per Protocol Analysis Set (PP)**

This will include all subjects who are randomized, received at least 1 dose of study medication, completed the study and do not have exclusionary major protocol deviations. Major and exclusionary protocol deviations will be defined in this SAP and by clinical review prior to unblinding.

#### **PK Analysis Set (PKAS)**

This will include all subjects who are randomized, received at least 1 dose of study treatment and have at least 1 quantifiable PK sample and do not have exclusionary major protocol deviations. The PKAS will be used to analyze the PK endpoints unless otherwise specified in the SAP. Major and exclusionary protocol deviations will be defined in this SAP and by clinical review prior to unblinding.

### **Determination of Sample Size**

A sample size of 28 subjects per treatment arm will have 90% power to detect a difference in mean change from baseline in trough FEV1 of 150 mL between GSP304 and GSP304 placebo assuming a 2-sided alpha of 5% and a standard deviation (SD) of 170 mL. These assumptions are based on available literature from similar studies conducted for Spiriva® Respimat®.

Given the overall 1:1:1:1:1 study treatment allocation ratio, 140 subjects are required for the analysis of the primary endpoint. Assuming a dropout rate of 10%, a total of 155 subjects (31 subjects per treatment arm) will be randomized.

This sample size is also considered to be sufficient for the relative bioavailability endpoint.

### **Pharmacodynamics Analyses**

The PD comparisons will be made between each dose of GSP304 and GSP304 placebo as well as Spiriva and Placebo.

#### **Analysis of Primary Pharmacodynamics Endpoint.**

Change from baseline in trough FEV1 at 24-hours after the last dose of treatment on Day 21 in comparison to GSP304 placebo. The primary endpoint measures the change from baseline (Day 1) at Day 21 (Week 3) in trough FEV1 response at approximately 24 hours after the last dose (average of 23 hours 15 minutes and 23 hours 45 minutes post-dose measurements). This will be analyzed using a Mixed-effect Model Repeated Measure (MMRM) model to produce treatment differences for each dose of GSP304 vs GSP304 placebo. The MMRM model will include the trough FEV1 assessment on day 1 and pre-dose data from all visits (Days 7, 14, and 21, which are the trough FEV1 assessments on days 6, 13 and 20) and fixed terms for treatment, visit, baseline, center, treatment by visit and baseline by visit interactions. The adjusted means for each treatment and the estimated treatment differences for the treatment comparisons will be presented together with 95% confidence intervals (CIs). Multiple imputation-based methods will be considered as a sensitivity analysis for missing data, with further detail provided. The primary endpoint will be analyzed using the FAS and primary inference will be based on Day 21 trough values. A sensitivity analysis will be based on the Full Analysis Set.

#### **Analysis of Secondary Pharmacodynamics Endpoints**

Analysis of secondary PD endpoints will be performed on the FAS.

Change from baseline in peak FEV1 within 12 hours post dose on Day 1 and Day 21: This endpoint measures the peak FEV1 from the serial readings taken through 12 hours post-dose and then calculates the change from baseline. The change from baseline will be analyzed using MMRM in a similar way to that of the primary endpoint to produce treatment differences for each dose of GSP304 versus GSP304 placebo.

Change from baseline (Day 1) at Day 21 (Week 3) in trough FVC response at approximately 24 hours after the last dose (average of 23 hours 15 minutes and 23 hours 45 minutes post-dose measurements) will be analyzed using MMRM in a similar way to that of the primary endpoint to produce treatment differences for each dose of GSP304 versus GSP304 placebo.

Change from baseline in time-normalized area under the curve for FEV1 measured over 12 hours on Day 1 and Day 21: The endpoint measures a series of FEV1 readings taken within 12 hours of dosing.

The trapezoidal rule will be used to calculate AUC0-12h and then normalized to the length of time. The change from

baseline will be analyzed using MMRM in a similar way to that of the primary endpoint to produce treatment differences for each dose of GSP304 versus GSP304 placebo.

All PD data will also be displayed in summaries and listings.

Time to steady-state: This is the time period from the first dose to two consecutive similar trough FEV1 or FVC measurements. The trough values will be tabulated and plotted by time for each active dose and placebo.

Time to onset of action (of both a 12% increase and 200 mL increase in FEV1 within 12 hours of dosing): This is the time period from the first dose to first onset of at least 12 percent and 200 mL improvement in FEV1 over the baseline value. The trough values will be tabulated and plotted by time for each active dose and placebo.

### **Pharmacokinetic, Pharmacogenomics, and Other Biomarker Analyses**

#### **Pharmacokinetic Analyses**

Pharmacokinetic analysis will be performed using the PKAS.

**Plasma:** Individual subject plasma PK parameters will be determined from plasma concentrations using non-compartmental methods for each subject. Actual collection times will be used for the analyses.

**Urine:** Amount and fraction of dose of tiotropium excreted in urine during the collected time interval in individual subjects will be estimated. Nominal collection times and urine volumes will be used for the estimation.

Additional parameters may be evaluated depending on the data obtained during the study. The derived PK parameters will be listed by treatment, subject and day and summarized by treatment and day. Wherever appropriate, data will be visualized by means of graphical representations. For the summaries, descriptive statistics for all relevant PK parameters will include: n, arithmetic mean, SD, coefficient of variation (%CV), geometric mean, geometric mean %CV, median, minimum and maximum. The plasma concentrations and amount in urine of tiotropium will also be listed by subject, summarized by treatment, and presented graphically as mean plots, and spaghetti plots.

#### **Statistical Analysis of Pharmacokinetic Parameters**

An analysis of variance (ANOVA) will be performed on the ln-transformed PK parameters AUC0-tauSS, and CmaxSS. The ANOVA model will include treatment as fixed effect. The results from the model will be back-transformed and the adjusted geometric means for each treatment and the estimated treatment ratios for the treatment comparisons will be presented together with 90% CIs.

The ratios and corresponding 90% CIs will be expressed as a percentage.

The following comparisons will be made:

GSP304 (tiotropium bromide) Inhalation Solution, [REDACTED]

GSP304 (tiotropium bromide) Inhalation Solution, [REDACTED]

GSP304 (tiotropium bromide) Inhalation Solution, [REDACTED]

For GSP304, dose-proportionality of tiotropium CmaxSS and AUC0-tauSS parameters will be assessed using a power model (linear regression relating log-transformed CmaxSS and AUC0-tauSS to the log-transformed dose). Estimates of the mean slopes of log-transformed dose will be reported along with corresponding 90% CIs. Dose proportionality will also be assessed based on amount of tiotropium excreted in urine.

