#### **6.5.4. Pharmacokinetic Set (PKAS)**

This will include all subjects who are randomized, received at least 1 dose of study treatment and have at least 1 quantifiable PK sample and do not have exclusionary major protocol deviations. The PKAS will be used to analyze the PK endpoints unless otherwise specified in this SAP. Major and exclusionary protocol deviations will be defined in section 7.3 and by clinical review prior to unblinding.

Subjects or data may be excluded from the PKAS at the discretion of the PK Scientist upon consultation with the sponsor. Any data excluded will be discussed in the CSR. Any excluded subject will have his or her concentration and PK parameter data (if available) listed only. Subjects who receive placebo will not be part of the PKAS. The PKAS will be used for all tables and graphical summaries of the PK data

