### **8.3. Statement of the Null and Alternative Hypotheses**

No formal hypothesis testing will be conducted for the primary pharmacokinetic endpoints.

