### **8.4. Analysis of the Primary Pharmacokinetic Endpoints**

The primary endpoint,  $AUC_{0-\text{tauSS}}$ , and  $C_{\text{maxSS}}$ , will be analyzed using an analysis of variance (ANOVA) model. An ANOVA will be performed on the ln-transformed  $AUC_{0-\text{tauSS}}$ , and  $C_{\text{maxSS}}$ . The ANOVA model will include treatment as fixed effect. The results from the model will be back-transformed and the adjusted geometric means for each treatment and the estimated treatment ratios for the treatment comparisons will be presented together with 90% CIs. The ratios and corresponding 90% CIs will be expressed as a percentage. The following comparisons will be made:

- GSP304 █ vs Spiriva® Respimat®
- GSP304 █ vs Spiriva® Respimat®
- GSP304 █ vs Spiriva® Respimat®

The statements of a SAS® PROC MIXED analysis would be:

```
PROC GLIMMIX data=dataset;
  CLASS subject dose;
  MODEL log_normliased_pk_parameter= dose / ddfm=kr link=log;
  RANDOM intercept /subject= subject;
  ESTIMATE 'GSP1 vs Spiriva' dose 1 0 0 -1 /cl alpha=0.1;
  ESTIMATE 'GSP2 vs Spiriva' dose 0 1 0 -1 /cl alpha=0.1;
  ESTIMATE 'GSP3 vs Spiriva' dose 0 0 1 -1 /cl alpha=0.1;
  LSMEANS dose/diff cl ilink alpha=0.10
RUN;
```

The back-transformed and adjusted means for each treatment and the estimated treatment differences for the treatment comparisons will be presented together with 90% confidence intervals for the treatment comparisons. The adjusted means and estimated treatment differences for the treatment comparisons will also be plotted, with corresponding 90% confidence intervals.

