### **Duration of nebulization**

Upon review of the tables, figures and listings produced at the end of the study, an exploratory analysis may be performed to evaluate the effect of duration of nebulization on primary and/or secondary outcomes if deemed appropriate following review of the summary data and nebulization times. The decision to perform this analysis will be made by the Sponsor. If the decision is made not to proceed, this section of the SAP will not be applicable and the outputs described herein will not be presented.

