## **9.3. Testing Statistical Assumptions Including Comparability at Baseline**

All baseline data will be summarized by treatment group using descriptive statistics. No formal hypothesis testing will be conducted. Differences may occur by chance. If there are any clinically meaningful differences identified, analyses may be adjusted to account for these imbalances through inclusion of additional covariates in the statistical models.

The PD endpoints (FEV1, FVC) are assumed to be normally distributed and will be analyzed under this assumption. The assumptions of normality and constant variance will be verified using diagnostic plots (normal quantile plots and scatter plots of residuals by treatment group). If assumptions are violated, either an appropriate transformation will be used or data will be analyzed using non-parametric methods. The methods used will be documented in the clinical study report.

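### Minor, cheap improvement: give the primary bioavailability ANOVA a separate residual variance per treatment, because one pooled variance over two devices leaves the 90% CIs unprotected if exposure spread differs

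*SAP*

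**What the plan says.** The synopsis (Statistical Analysis of Pharmacokinetic Parameters) and section 8.4 specify the same primary PK model, an ANOVA of ln AUC0-tauSS and ln CmaxSS: "The ANOVA model will include treatment as fixed effect". For the three GSP304-versus-Spiriva comparisons, "the estimated treatment ratios for the treatment comparisons will be presented together with 90% CIs".

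Section 6.5.4 limits the model to four arms: "Subjects who receive placebo will not be part of the PKAS". Section 8.3 adds: "No formal hypothesis testing will be conducted for the primary pharmacokinetic endpoints".

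The code in 8.4 is introduced as PROC MIXED but prints PROC GLIMMIX with "MODEL log_normliased_pk_parameter= dose / ddfm=kr link=log" and "RANDOM intercept /subject= subject". Neither statement lets the variance differ by arm.

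On assumptions, 9.3 says "The assumptions of normality and constant variance will be verified using diagnostic plots" and adds a fallback, but that paragraph concerns the PD endpoints FEV1 and FVC. Section 8 has no counterpart for the PK endpoints. Section 8.5 allows for an optional analysis to "evaluate the effect of duration of nebulization on primary and/or secondary outcomes". No PK standard deviation or CV appears anywhere. Section 4.3.1 only asserts that the sample size is enough for relative bioavailability.

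**The concern.** A pooled ANOVA gives all three ratios the same variance. With equal arm sizes, one quarter of it comes from Spiriva, one quarter from the GSP304 dose being compared, and half from the two doses that are not in the comparison. If ln-scale spread differs between arms, the nominal 90% interval is not a 90% interval.

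Three features of the SAP make unequal spread plausible:

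- The products use different devices, a nebuliser and a soft mist inhaler.
- Nebulisation time varies only in the GSP304 arms, and 4.5 times all post-dose samples from the end of dosing.
- Section 6.7.6.2 allows for the last quantifiable sample falling before 24 hours in more than half of the subjects at a given dose. That could add dose-specific noise to AUC.

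With no PK test planned, the ratio and its interval are what the first primary objective delivers, and the interval is its statement of uncertainty. Per-treatment geometric %CV (8.2) would reveal unequal spread, but no rule says what follows. A change of model after unblinding would be post hoc.

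**Working it through.** **The plan's own figure.** The only computed sample size is for trough FEV1: 150 mL difference, SD 170 mL, two-sided 5%, 28 per arm. The noncentral t power is 0.9001, so the stated 90% reproduces. It says nothing about PK precision; it only supplies the 28 per arm used below.

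**Inputs.** Four arms, n = 28 each, pooled df = 4 × 27 = 108, t(0.95; 108) = 1.659. The ln-SDs are assumptions, since the SAP gives none. By 8.2's formula, CV = 100 × √(exp(SD²) − 1), ln-SDs of 0.3, 0.4, 0.5, 0.6 and 0.7 are CVs of about 31%, 42%, 53%, 66% and 80%.

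**Formula.** Pooled variance s² = (σ₁² + σ₂² + σ₃² + σ_S²)/4. The model attributes 2s²/n to the log ratio of dose i to Spiriva; the true variance is (σᵢ² + σ_S²)/n. The standard error is therefore off by the factor r = √[2s²/(σᵢ² + σ_S²)], and coverage is roughly 2Φ(1.659 r) − 1.

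**Moderate differences.**

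- GSP304 0.5, Spiriva 0.4: s² = (3 × 0.25 + 0.16)/4 = 0.2275; r = √(0.455/0.41) = 1.053; approximate coverage 0.92.
- GSP304 0.4, Spiriva 0.5: s² = (3 × 0.16 + 0.25)/4 = 0.1825; r = √(0.365/0.41) = 0.943; approximate coverage 0.88.

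**Large differences.**

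- GSP304 0.3, Spiriva 0.6: s² = 0.1575; r = √(0.315/0.45) = 0.837.
- GSP304 0.6, Spiriva 0.3: s² = 0.2925; r = √(0.585/0.45) = 1.140.
- One dose 0.7, other arms 0.4: s² = 0.2425; r = √(0.485/0.65) = 0.864 for that dose and √(0.485/0.32) = 1.231 for the other two.

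**Simulation** (200,000 trials per scenario, 28 per arm):

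| ln-SD, GSP304 / Spiriva | Pooled coverage | Separate-variance coverage |
|---|---|---|
| 0.4 / 0.4 | 0.90 | 0.90 |
| 0.5 / 0.4 | 0.92 | 0.90 |
| 0.4 / 0.5 | 0.88 | 0.90 |
| 0.6 / 0.3 | 0.94 | 0.90 |
| 0.3 / 0.6 | 0.83 | 0.90 |
| 0.7, 0.4, 0.4 / 0.4 | 0.84 for the 0.7 arm; 0.96 for the others | 0.90 |

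A second set of runs on the CV scale agrees. GSP304 60% against Spiriva 40% gives 0.925, and the reverse gives 0.865. With 31 per arm the results move by no more than about 0.002. When all variances are equal, the pooled interval is 0.993 times the width of the separate-variance one, so separate variances cost about 0.7%.

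**Text against code.** The text describes an ANOVA of ln exposure, whose contrasts are differences of ln means and back-transform to ratios. The code puts a log link on a response already named as logged, so its contrasts are on the log of the mean ln value and are not ln ratios of exposure. Each subject has one steady-state value per parameter, so the random subject intercept cannot be separated from the residual. The block does not fit the stated ANOVA whichever variance structure is chosen.

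**The case against.** Pooled ANOVA on ln exposure is conventional, and the SAP nowhere says that spread differs by arm. The log transform already removes proportional scaling, so a higher dose alone does not raise the variance. Allocation is balanced, the ratio estimates do not depend on pooling, no pass/fail decision rests on the intervals, and planned per-arm geometric %CV and individual plots would show unequal spread. All of this stands, and it is why the point is minor.

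Three stronger readings are tempting but unsupported:

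- **That the primary intervals are wrong as written, or cover only 83%.** That figure needs Spiriva to have twice the ln-SD of the nebulised arms, which nothing in the SAP supports. Extra variability from nebulisation time would make GSP304 the more variable product, and the intervals then come out too wide.
- **That the error necessarily differs by dose.** It does so only if the GSP304 arms differ among themselves. The 6.7.6.2 provision is a contingency, not a forecast. It concerns how complete AUC is, already offers AUClast in response, and gives no evident reason for unequal variance in CmaxSS.
- **That one added line of code suffices.** The printed block has to be replaced.

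The objection leaves two things untouched: the PK endpoints have no variance check or fallback, although FEV1 and FVC do, and balanced allocation does not remove the effect, because each ratio uses only two of the four pooled arms.

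**Conclusion.** A cheap improvement of minor severity, not an error in the plan. One residual variance serves all four arms and no PK safeguard is written. Any consequence is confined to the calibration of the 90% CIs and depends on a variance difference that the SAP neither states nor quantifies. For a moderate difference (ln-SD 0.5 against 0.4) coverage is about 0.92 or 0.88, depending on which product is more variable, with intervals about 5% too wide or 6% too narrow. The range 0.83 to 0.96 arises only under twofold or near-twofold SD differences. These figures assume ln-normal exposure and 28 subjects per arm. The case for acting is the asymmetry: almost no cost if variances are equal, correct coverage if they are not, and a code block that needs rewriting anyway.

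**What to change.** In 8.4 and the synopsis, keep treatment as the only fixed effect on ln AUC0-tauSS and ln CmaxSS, and add that a separate residual variance is estimated for each treatment. Replace the GLIMMIX block with PROC MIXED on the ln-transformed parameter: treatment in MODEL, REPEATED / GROUP=treatment, Satterthwaite or Kenward-Roger degrees of freedom, no link function and no random subject intercept. Exponentiate the estimates and 90% limits to give the ratios as percentages. Make the change before unblinding.

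The cost is one SAP sentence in each place, a rewritten code block, and intervals about 0.7% wider if the variances are in fact equal.
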